8.3.1 Multi-center Studies

Participants for this study will be recruited from a single site: Cincinnati Children’s Hospital Medical Center.

[figure not shown]
8.4 Missing Data

Although every effort will be undertaken to eliminate missing data, driving simulator and DriveCam equipment failures could occur, and the possibility exists that participants may not complete follow up assessments even after prompting from the research team. Missing data will be assumed to be minimal (< 15%), missing at random (MAR), and consistent with Intent-to-Treat analyses handled via multiple imputation in all primary outcomes analyses (see below for multiple imputation models description).

Primary Analyses

Two different types of multiple imputation models, data analysis model-based imputation, and fully-conditional specification imputation (Enders, 2010; Graham, 2012; Muthén & Muthén, 1998-2017, p. 576), were used to handle primary analysis missing data because the two primary outcomes were measured on two different scales. Missing data for standard-deviation of lane-position, a continuous response variable, was handled using model based imputation assuming a normal distribution. Specifically, a model in which specific driving simulator “runs” (level 1) nested within drive types over time (level 2) across participants (level 3) formed the foundation of the missing data imputation model. A binary indicator of the specific driving simulator “run” was the sole level 1 predictor of standard-deviation of lane-position (“DV”), and that effect was allowed to vary across driving types at level 2 (i.e., slope variance; “RUN1VAR”). Binary indicators of 1-month (“DriveType_1”) and 6-month (“DriveType_2”) predicted both standard-deviation of lane-position (“DV”) and the variation in the effect of specific “run” as a predictor of standard-deviation of lane-position (“RUN1VAR”) at level 2, and all four of those predictive effects (shown as “Dr1_DV”, “Dr2_DV”, “Dr1_Run1”, “Dr2_Run1”) were allowed to vary across participants at level 3. Randomization (“TxGroup”) was entered as a level 3 predictor of all 5 sources of variance (“Run1Var”, “Dr1_DV”, “Dr2_DV”, “Dr1_Run1”, “Dr2_Run1”). Driving experience, a level 3 covariate, was included in the model as a predictor of standard-deviation of lane-position (“DV”) variance across participants. The standard-deviation of lane-position multiple imputation model is represented graphically in the figure below.

Trial of Training to Reduce Driver Inattention in Teens with ADHD

Missing data for long-glances, a Poisson-distributed count response variable, could not be imputed with the same 3-level model used to impute missing standard-deviation of lane-position data. Currently, there is no statistical analysis software package capable of imputing missing 3-level count response variable data. In fact, only Mplus (version 8.8) is capable imputing missing multilevel count data, but only under two conditions: 1.) the imputation model can have no more than two levels, and 2.) missing count of long-glances data can only be imputed with a fully conditional specification (or H_A) model. As such, the multiple imputation model used to handle missing long-glance data is different from the imputation model used to handle missing standard-deviation of lane-position data in two ways: 1.) a 2-level imputation model, where long-glances variation in driving “runs” nested within post-baseline “drive types” constituted the level 1 model, and long-glances variation across participants constituted the level 2 model, and 2.) all available analysis variable information (i.e., means, variances [where applicable], and covariances [where applicable]) at both levels was used to impute missing long-glances data.

$M = 100$ imputed datasets were generated for all multiple imputation models. Imputed standard-deviation of lane-position and long-glances primary outcomes data were analyzed using generalized estimating equations (GEE) allowing response variable data non-independence from “runs” nested within “drive types” across participants to be modeled. Specifically, the standard-deviation of lane-position GEE model was specified using a normal distribution assumption with an identity link function. The GEE for long-glances, a count variable, was modeled specifying a Poisson distribution and a natural logarithmic link function. All primary and secondary GEE analyses of imputed data pooled the estimates based on Rubin’s rules, and all standard errors were computed based on the average standard errors across imputations and the parameter estimate variation across imputations (Rubin, 1987; Schafer, 1997).

Secondary Analyses

The two outcomes for the secondary analyses, off-road glances and crash/near crash were both measured on a binary scale. Some participants did not have any events either due to the DriveCam not being installed in their car or they did not have any events. Such missing data was not imputed, and we conducted non intent-to-treat analysis using those participants with event data. There was no missing data for the ‘crash/near crash’ secondary outcome across events for those with a DriveCam installed. The GEE analysis for the ‘crash/near crash’ outcome was performed using all

participants with DriveCam event data available. However, long glance data was missing for some events due to unforeseen circumstances (e.g., DriveCam view obstruction or participant driver was wearing sunglasses). Missing data for the 'long-glance' outcome was imputed using GEE model-based imputation. Specifically, a logistic link function was used within a missing data imputation model that allowed the effect of random assignment to predict the presence (=1) or absence (=0) of long-glances nested within participants while controlling for months of driving experience and days DriveCam was operational in vehicle.

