
5.f Analyses

5.f.1 Missing Data: Although every effort will be made to avoid having missing data when a teen withdraws from the study or a data point is missed, missing data due to attrition is common in longitudinal studies. *However, as noted in Section 5.a.6, we have demonstrated high rates (>90%) of retention in other*

ADHD treatment studies. That said, if a participant drops from the study, we will replace that participant with a new participant in order that we are adequately powered to test our study hypotheses. Moreover, we will utilize maximum likelihood estimation to address data assumed missing at random. A missing data attrition analysis will be performed using SAS PROC MI to identify potentials for non-random or systematic attrition (MNAR) related to key independent and dependent variables. In cases of MNAR missing data, selection and pattern mixture models will be used to appropriately address non-random attrition.

5.f.2 Analyses

5.f.2.a Analytic Plan to Address Aims 1 & 2

Aim #1: Examine short- and long-term efficacy of FOCAL+ intervention on decreasing rates of extended glances away from the roadway among teens with ADHD

Hypothesis #1: *Teens with ADHD assigned to the FOCAL+ intervention will evidence fewer extended glances away from roadway immediately following initial training, and 1-, 4-, 8- and 12-months post randomization compared to teens with ADHD assigned to the sham intervention.*

Aim #2: Examine short- and long-term efficacy of FOCAL+ intervention on improving driving performance among teens with ADHD

Hypothesis #2: *Teens with ADHD in FOCAL+ will exhibit more improvements in driving performance immediately following initial training, and 1-, 4-, 8- and 12-months post randomization than teens with ADHD in the sham intervention group.*

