2) Crashes and near crashes (CNC): Like the extended eye glance endpoint, this variable is only calculated when participants experience a g-force event $\geq .6$. Coders will record whether the event captured a crash (i.e., contact between the vehicle and another object) or near crash (i.e., an evasive maneuver performed to avoid a MVC). Some participants may not contribute data due to not having any events. These participants will not be included in analyses. The lower end of the range for this variable, for participants who do experience at least 1 .6 g-force event during the observation period is 0. There is no upper limit to this variable.

7 Sample Size

Our initial protocol proposed to randomize 136 participants; however, this randomization goal did not account for attrition at the 1- and 6-month driving simulations—the source of our primary endpoints. When we reached a sample size of 136, we estimated how many additional participants would be required to achieve 136 participants with completed driving simulation data at 1- and 6-months post-training. The calculation suggested that we needed to recruit a randomized sample size of 152 to achieve 136 participants with 1- and 6-month simulator outcomes (primary endpoints). (See Section 16 for date of this protocol change).

8 General Analysis Considerations

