8.2 Analysis Populations

8.2.1 Full Analysis Population (or Intention to Treat or Modified Intention to Treat)

- All subject who were randomized.
- Driving simulation outcomes: All participants will have baseline driving simulation. Missing driving simulation data at the 1-month and 6-month timepoints will be assumed to be missing at random and handled using multiple imputation.
- Demographic characteristics: All participants who are randomized will be included in the report of demographic characteristics of the sample.

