9.10 Treatment Compliance

The number of treatment sessions attended will be used to assess treatment compliance.

10 Efficacy Analyses

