c. Change in correction for type I error. We initially proposed to use false discovery rate to control for type I error. However, the statistical expert reviewer indicated that Bonferroni corrected alpha is more a more appropriate type I error control in confirmatory studies of a small number of pre-specified hypotheses. Accordingly, we used a Bonferroni corrected alpha threshold of 0.0125 for assessing statistical significance of the four primary outcome measures at 1-month and 6-months.

d. Change in covariate. Rather than use years since licensure as a covariate, we now use months of driving experience instead of years of experience in all our analyses.

e. Change in handling of missing data. Multiple imputation was used (See 8.4 Missing Data for more details) to handle missing data rather than maximum likelihood estimation.

2) Addition of supplemental analyses.

a. Sensitivity analysis of naturalistic driving results including only teens whose 1-year of naturalistic driving ended prior to COVID restrictions. Of the 152 participants, 56 (FOCAL+: n=29 teens; Sham Control: n=27 teens) participants had a portion of their 1-year of naturalistic driving that included days beyond March 15, 2020, when COVID restrictions were put into place. We conducted a sensitivity analysis of our naturalistic driving results including only the 96 teens (FOCAL+ n=47; Sham Control n=49) whose 1-year of naturalistic driving ended prior to COVID restrictions.

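### Primary-endpoint imputation assumes MAR without using sessions attended, and the SAP lacks the protocol's non-random-attrition check, so the intention-to-treat effect may be modestly overstated

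*Combined protocol and SAP*

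**What the plan says.** **Assumption.** SAP 8.2.1 puts every randomised teen in the full analysis population and adds: "Missing driving simulation data at the 1-month and 6-month timepoints will be assumed to be missing at random and handled using multiple imputation". SAP 8.4 repeats this for all primary outcomes: "Missing data will be assumed to be minimal (< 15%), missing at random (MAR), and consistent with Intent-to-Treat analyses handled via multiple imputation".

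**Imputation models (SAP 8.4).** For SDLP, a three-level model contains run, the 1- and 6-month indicators with effects varying by participant, arm, and driving experience as the only named covariate. For long glances, a two-level model is used in which "all available analysis variable information (i.e., means, variances [where applicable], and covariances [where applicable]) at both levels was used to impute" the missing counts. Sessions attended is not among the analysis variables of the primary efficacy model (SAP 10.5).

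**Attendance.** It is recorded, but its only stated use is in SAP 9.10: "The number of treatment sessions attended will be used to assess treatment compliance". SAP 9.5 counts training as completed after at least one session. SAP 5.2 starts the follow-up clock at the last session completed.

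**Non-random attrition.** Protocol 5.f.1 planned an analysis to look for systematic attrition, and then: "In cases of MNAR missing data, selection and pattern mixture models will be used to appropriately address non-random attrition". The SAP contains neither step. The logged missing-data change (SAP 14.7, 06/23/2022) reads: "Multiple imputation was used (See 8.4 Missing Data for more details) to handle missing data rather than maximum likelihood estimation". The supplemental analyses kept on 08/15/2022 are medication moderation and the COVID-19 sensitivity analysis.

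**The concern.** The documents themselves treat the number of sessions as relevant to benefit. Protocol 3.g expects teens with ADHD to need more than one session, 5.a.5 reports that extended glances persisted after a single FOCAL+ session, and Aim 3 asks how many sessions are needed. SAP 14.5 records no change of aims. They also expect behavioural attrition: SAP 8.5.6 explains the uncertainty about drop-out by the difficulty this population can have in keeping commitments.

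A teen who abandons training may thus be both more likely to miss the simulator visit and less improved. If the variable linking the two is left out of the imputation model, MAR becomes doubtful, and a missing FOCAL+ teen is filled in largely as an assessed FOCAL+ teen with similar observed data would be. The estimate is presented as intention-to-treat but moves toward the effect that would be seen had everyone stayed in training. No analysis in the SAP shows how far the four primary conclusions depend on this.

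**Working it through.** **The plan's own figure.** SAP section 7 says "we needed to recruit a randomized sample size of 152 to achieve 136 participants with 1- and 6-month simulator outcomes". It states no attrition rate, so 152 can only be back-solved, not reproduced. From 136/(1 − d) = 152, d = 16/152 = 10.5%. For comparison, 136/0.85 = 160, so 152 is consistent with the SAP's assumption of under 15% missing. If the 136 are teens with both visits, 10.5% is an upper bound on missingness at either visit alone.

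**Inputs**
- m, share of FOCAL+ teens missing: 10.5% or 15%. *Assumption*: the documents give no split by arm.
- f, share of the average assessed FOCAL+ benefit that missing teens really have: 0, 0.5 or 0.75. *Assumption*: not in the documents. At f = 0 they look like sham teens.
- δ, between-arm difference among assessed teens: 0.6 − 0.10 = 0.5 SD (protocol 5.f.2.a.1). The percentages below do not depend on δ.
- Alpha: 0.05/4 = 0.0125 per test (SAP 8.5.5), taken as two-sided.

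**Formula.** Imputation within arm returns about δ. The effect in all randomised teens is δ × [1 − m(1 − f)], so the relative overstatement is 1/[1 − m(1 − f)] − 1.

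| m | f | All-randomised effect (SD) | Overstatement |
|---|---|---|---|
| 10.5% | 0 | 0.447 | 11.8% |
| 10.5% | 0.5 | 0.474 | 5.6% |
| 10.5% | 0.75 | 0.487 | 2.7% |
| 15% | 0 | 0.425 | 17.6% |
| 15% | 0.5 | 0.463 | 8.1% |
| 15% | 0.75 | 0.481 | 3.9% |

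These are differences in means. For the glance rate ratio, read them as applying to the difference in mean counts.

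**Simulation check.** Imputing a single visit from arm and own baseline at m = 10.5% gave 0.498 against a true 0.446 (f = 0), and 0.502 against 0.476 (f = 0.5). If 10% or 20% of the *assessed* FOCAL+ teens are also partly trained with no benefit, the imputed effect falls to 0.447 or 0.401, against a true 0.400 or 0.359.

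**Other reasons for missing.** If only half of the missing FOCAL+ teens had stopped training (assumption), m in the formula is 10.5%/2 = 5.3%. The overstatement is then 5.6% at f = 0 and 2.7% at f = 0.5.

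**Imbalance by arm.** In the extreme case of all 16 missing teens in FOCAL+ (16/76 = 21.1%, 76 per arm under 1:1 allocation) with no benefit, the effect is 0.5 × 0.789 = 0.395, an overstatement of 1/0.789 − 1 = 27%. Nothing in the documents suggests this. It shows why missingness by arm must be reported.

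**Consequence for a test.** A plain single-visit comparison at two-sided alpha 0.0125 with 76 per arm, ignoring baseline and the second run, has power 0.72 at 0.50 SD, 0.66 at 0.474 and 0.60 at 0.447. The shift could decide a borderline test.

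**The case against.** **Fully trained donors.** A reader might infer that FOCAL+ drop-outs are given the benefit of fully trained teens. The documents do not support that. The imputation draws on all assessed FOCAL+ teens, who can include partly trained ones, since follow-up is timed from the last completed session. A teen's own data also count: SAP 8.2.1 says every participant has a baseline drive, and the SDLP model lets the time effects vary by participant. The log entry for the sample increase is headed by the 6-month visit, and a teen missing only that visit brings an observed 1-month result. This stands, and it is why the claim is limited to the average assessed teen.

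**Wholly one-sided error.** That is also too strong. Sham teens receive rules-of-the-road training and yoked simulator drives (SAP 6.1), so sham drop-outs are credited with their arm's gain too. The protocol puts the sham effect at only 0.10 against 0.6, so the net lean probably still favours FOCAL+.

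**12% and 18% as the expected size.** They are ceilings for the stated missing shares, requiring that no missing FOCAL+ teen gained anything. SAP 8.4 names equipment failure as another cause of missing data.

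**A deliberate removal.** The protocol's models were conditional on evidence of non-random missingness, and no log entry says they were abandoned. What can be said is that the SAP contains neither the models nor the attrition analysis that would trigger them.

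**Existing safeguards.** The SAP tracks drop-outs with reasons (9.5) and reviews protocol deviations for possible statistical adjustment (9.7). These are useful inputs but do not replace a sensitivity analysis.

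**Conclusion.** The point holds in limited form. SAP 8.4 imputes every missing 1- and 6-month simulator outcome under MAR, leaves a recorded and plausibly relevant variable out of both models, and provides no check on departure from MAR although the protocol planned one. The likely direction is an overstated intention-to-treat effect.

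At 10.5% missing in FOCAL+ the overstatement is about 6% with half the benefit retained and at most about 12% with none. At 15% missing it is about 8% and at most 18%. These figures assume the missing share in FOCAL+ and the retained benefit, neither of which the documents give. They shrink if visits were missed for reasons unrelated to training and vanish if partial training gave the full average benefit. The multiplier 1 − m(1 − f) stays positive for any f from 0 to 1, so this mechanism alone would not reverse an effect. The change should be made, but the omission does not invalidate the primary analysis.

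**What to change.** In SAP 8.4:

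1. Add the number of training sessions attended as an auxiliary variable in both imputation models, by arm where enough low attenders have outcomes to support it. If few drop-outs were assessed, this step alone will not settle the matter.
2. Report missingness at each visit by arm, reason and sessions attended.
3. Restore the protocol's check on non-random attrition as one pattern-mixture sensitivity analysis for all four primary tests. Either sham-reference imputation for FOCAL+ teens who stopped training or a delta-adjusted tipping point would serve, with the same M = 100 imputations and the same GEE. Report it beside the MAR result, with no significance threshold for calling a claim robust. Much of 8.4 is already in the past tense, so label the analysis post hoc if the data are unblinded.
4. Record in 14.7 what became of the attrition analysis and the models in protocol 5.f.1.

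The cost is some analyst time and no new data collection. A reference-based estimate will be somewhat smaller than the MAR estimate.

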8.5 Interim Analyses and Data Monitoring

8.5.1 Purpose of Interim Analyses

The only planned interim analysis involves safety monitoring of DriveCam incident data. We will designate a researcher ([name]) independent of the present study who will be unblinded to treatment randomization. This researcher will examine the monthly report for events where trigger type = shock [indicative of a collision] and review those clips. Clips containing a crash will be recorded and frequencies by treatment group will be examined. The purpose of these interim safety analyses is to ensure that the FOCAL+ training is not associated with a greater proportion of crashes. If so, we will terminate the study.

8.5.2 Planned Schedule of Interim Analyses

The safety monitoring will occur monthly when we receive the event reports from Lytx.

8.5.3 Stopping Rules

Should participants in the FOCAL+ group experience disproportionately greater numbers of crashes, the independent researcher will inform the PI to determine whether the study will need to end early.

8.5.4 Analysis Methods to Minimize Bias

Generalized estimating equations allows data from driving simulation "runs" (2) within each of the three drive "types" (baseline, 1-month, & 6-month) for all participants to be modeled as correlated responses in analyses even though none of the potential effects for "runs" are of theoretical interest. Risk ratio effect sizes for secondary DriveCam response variables with 95% confidence intervals will be computed based on GEE analysis results.

8.5.5 Adjustment of Confidence Intervals and p-values

Because we have two primary endpoints (number of extended glances away from the roadway and SDLP during driving simulation) that are collected at 2 primary endpoints (1-month post-training and 6-months post-training), we have 4 statistical tests for our primary hypotheses. In order to control for potential Type 1 error, we will use a Bonferroni-corrected alpha of .0125 for testing statistical significance.

Confidence intervals for relative risk ratios effect sizes for the secondary DriveCam data analyses will be obtained based on GEE analysis results. Note that the widths of confidence intervals are not adjusted for multiple comparisons and no definite conclusions can be drawn from these results.

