5.f.2.a.1 Power Analyses for Testing Hypotheses 1 & 2: *Effect size estimates from our preliminary data (Section 5.a.5) suggest a single FOCAL+ training session improves extended eye glances among teens with ADHD with an effect size (Cohen's d) of 1.19. Since this effect size will surely diminish over the course of the 1-year of assessments, we used a conservative effect size estimate of .6 to power our research hypotheses. Monte Carlo simulation power analyses were performed under the following assumptions: (a) FOCAL+ effect size of .6, (b) effect size of .10 for our sham intervention, and (c) inclusion of months of driving experience as a covariate. Power analysis with these assumptions indicate that sample sizes of N = 41 per group will result in power $\geq .80$ to detect a significant main effect of Group indicating that the FOCAL+ intervention results in significantly fewer extended glances compared to the sham group at all post-baseline time points. We've powered our study with a larger sample size in order to detect potential moderators of treatment response (see Section 5.f.2.c below). Using the proposed sample size of 68 participants per group will provide use with 99% power to detect treatment effects.*

While data has been collected examining the efficacy of the FOCAL+ intervention on extended eye glances, the efficacy of the FOCAL+ intervention on driver performance has not been addressed. However, we assume a comparable intervention effect for FOCAL+ on driving outcomes based on the following pieces of evidence. Since the Pearson correlation between extended eye glances and collision events in the driving simulator is .74⁴², we will assume that the effect size for intervention effects on driving outcomes will be

comparable to what has been found for extended glances and that we will have >90% power to detect intervention effects on driving performance outcomes as well.

Aim #3: *Examine how many FOCAL+ training sessions are required to normalize extended glances away from the roadway among teens with ADHD.*

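### The four primary tests use single-step Bonferroni at .0125; Holm step-down gives the same guaranteed 5% family-wise control and can only reject as much or more

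*Combined protocol and SAP*

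**What the plan says.** SAP section 8.5.5 counts two primary endpoints (extended glances and SDLP in the simulator) at 1 and 6 months after training. It concludes that "we have 4 statistical tests for our primary hypotheses" and that "we will use a Bonferroni-corrected alpha of .0125 for testing statistical significance". No step-down, hierarchical or gatekeeping procedure is described. Section 8.6 (Multiple Testing) only cross-refers.

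Section 14.7, in the changes dated 06/23/2022, gives the history: "We initially proposed to use false discovery rate to control for type I error". The journal's statistical expert then advised that "Bonferroni corrected alpha is more a more appropriate type I error control in confirmatory studies of a small number of pre-specified hypotheses". The comparison recorded there is Bonferroni against false discovery rate. Holm is not mentioned.

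The only power calculation is in protocol section 5.f.2.a.1. It assumes "a) FOCAL+ effect size of .6, (b) effect size of .10 for our sham intervention" and states that "Using the proposed sample size of 68 participants per group will provide use with 99% power to detect treatment effects". For driving performance it assumes an effect "comparable to what has been found for extended glances and that we will have >90% power to detect intervention effects". It concerns one main effect of Group in the ANCOVA design that GEE later replaced, and it mentions no multiplicity correction.

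**The concern.** Single-step Bonferroni holds each test to .0125 whatever the other three show. Holm relaxes the threshold each time a hypothesis is rejected, with no added assumption about ordering or correlation. The reason recorded in section 14.7 is an argument for family-wise control in a small confirmatory family. Holm meets it equally well.

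The choice matters most when several effects are real, and that is what the plan expects. Protocol section 5.f.2 predicts superiority over sham at each time point, and 5.f.2.a.1 carries the glance effect over to driving performance. In that setting a 6-month or SDLP result could miss .0125 and be called non-significant when a procedure with the same guarantee would have accepted it.

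**Working it through.** **1. The plan's own alpha.** .05/4 = .0125, which reproduces exactly. The family-wise .05 is implied, not stated. With four independent true nulls the actual family-wise error is 1 − (1 − .0125)^4 = .0491.

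**2. Holm thresholds.** Ordered from the smallest p-value: .05/4 = .0125, .05/3 = .0167, .05/2 = .025, .05/1 = .05, stopping at the first failure. The first step equals Bonferroni's and later steps are looser, so every Bonferroni rejection is also a Holm rejection.

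**3. Inputs.** From the documents: effect sizes .6 and .10 (5.f.2.a.1), read as a net d = .6 − .10 = .5; 68 completers per arm (136 with simulator outcomes, SAP section 7, allocated 1:1). Assumed: two-sided tests, the same d on all four, one normal two-sample contrast per test, and the correlations among the tests, which the documents do not give.

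**4. Power per test under Bonferroni.** Mean of the statistic = d × √(n/2) = .5 × √34 = 2.915. The critical value at two-sided .0125 is 2.498. Power = Φ(2.915 − 2.498) = Φ(.418) = 66%. At d = .6: .6 × √34 = 3.499, and Φ(1.001) = 84%.

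**5. Bonferroni against Holm.** Four correlated normal statistics, 400,000 draws per setting, with correlation between time points/between endpoints of 0/0, .5/.3 and .7/.6. Ranges run across the three settings.

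| Scenario, 68 per arm | Quantity | Bonferroni | Holm |
|---|---|---|---|
| d = .5 on all four | per test | 66% | 75-77% |
| | all four | 19-40% | 45-61% |
| | at least one | 89-99% | identical |
| d = .6 on all four | per test | 84% | 90-92% |
| | all four | 50-66% | 77-83% |
| d = .5 on the two glance tests only | per glance test | 66% | 68-69% |
| | family-wise error (two true nulls) | 2.2-2.4% | 3.4-4.0% |
| No effect on any test | family-wise error | 4.0-4.9% | identical |

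With d = .5 throughout, Bonferroni therefore costs 9-11 points per test and 21-26 points for all four, and nothing for at least one.

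**6. When Holm rescues a p-value above .0125.** It depends on the other tests. A p of .015 needs at least one other test rejected, .02 needs at least two, and .04 needs all three.

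**7. Does the stated 99% cover this?** One two-sample contrast at two-sided .05 with d = .5 and 68 per arm has Φ(2.915 − 1.960) = 83% power. About 99% is reached if 4-5 time points are averaged with an assumed correlation near .3. For five, the variance factor is (1 + 4 × .3)/5 = .44 and Φ(2.915/√.44 − 1.960) = Φ(2.43) = 99%. That describes a pooled Group effect, not four tests at .0125.

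**The case against.** The case for leaving the rule alone has several parts.

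- **Bonferroni is valid, and the choice is documented.** Both are true. A reader might infer that section 8.5.5 contains an error, but it does not: this is a question of efficiency. The recorded advice rejects false discovery rate and gives no ground for preferring Bonferroni to Holm.
- **Timing.** The rule was set on 06/23/2022 in response to journal review. Moving to Holm would be a third multiplicity method, with looser thresholds, possibly after the p-values were seen. This stands, and it limits the fix.
- **Error control is not identical in practice.** With two true nulls, family-wise error is 2.2-2.4% under Bonferroni and 3.4-4.0% under Holm. Bonferroni also bounds the expected number of false rejections at .05, which Holm does not. A reader might infer that Bonferroni buys nothing in error control. That is so only for the guaranteed 5% bound.
- **The larger gains belong to a favourable case.** Equal effects on all four tests suit Holm. Section 5.f.2.a.1 concedes that the effect on driving performance had not been studied, and 5.f.2 expects the strongest effects at 1 month. No success rule in the documents requires all four tests to be significant. These points stand, which is why the 2-3 point scenario belongs beside the others.
- **The model differs.** The primary tests are GEE Group × Timepoint interactions, with a Poisson log link for glances (section 10.5), so the percentages are only approximate. Holm's ordering over Bonferroni does not depend on the model.
- **Intervals.** Bonferroni has simple matching 98.75% intervals and Holm does not. This stands, although section 10.5 promises intervals for the primary endpoints without naming a level.

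**Conclusion.** The point holds as a cheap improvement to a valid plan. Holm gives the same guaranteed 5% family-wise bound under any dependence and never rejects less. Under an equal net effect of 0.5 SD on all four tests, 68 per arm, it adds 9-11 points of power per test and 21-26 points for winning all four. If only the glance effects are real it adds about 2-3 points, and it never changes the chance of at least one significant test. These sizes rest on normal approximations, two-sided testing and assumed correlations.

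Two stronger readings should be resisted. One is that any true effect with p between .0125 and .05 is lost because of Bonferroni; Holm recovers such a result only when enough of the other tests are rejected first. The other is that the trial is shown to be underpowered. The documents never define success as all four tests, and they do not give the variances and correlations needed to compute power for the actual GEE tests.

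**What to change.** **If the primary results are not yet known:** replace the Bonferroni sentence in section 8.5.5 with a statement that the four primary p-values will be tested by the Holm step-down procedure at family-wise alpha .05. Report Holm-adjusted p-values, and show 98.75% intervals for the primary effects, labelled as conservative.

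**If they are already known,** which the date and setting of the 06/23/2022 change suggest but the documents do not state outright: keep Bonferroni at .0125 as the formal rule. Add Holm-adjusted p-values as a labelled sensitivity analysis, with its date recorded in section 14.7.

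The cost is one sentence or one extra column of p-values. The downside is that simultaneous intervals matching Holm decisions are less simple, so a Holm rejection can sit beside a 98.75% interval that includes no effect. A footnote should say so.
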